10.3 Withdrawal from Protocol for Lack of Efficacy

The Treating Physician may choose to withdraw the subject from the protocol for lack of efficacy and to initiate rescue (alternative) therapy for ML or CL.

For CL, the basis for lack of efficacy will generally be failure of at least one lesion: lesion has worsened at the end of therapy or thereafter, OR does not Improve at the Week 6 or Month 3 visit, OR is not healed at the Month 7 visit, OR relapses, or a new lesion.

For ML, the basis for lack of efficacy will generally be failure: clinically worse (by MSS score) at the Week 6 visit of or thereafter, OR does not improve at the Month 3 or Month 6 visit, OR is not healed at the Month 13 visit, OR relapses.

11 SAFETY/ADVERSE EVENTS

11.1 Assessment Methods

11.1.1 Symptoms

Medical history: At screening, during treatment, and during follow up, subjects will be asked general questions about their well being and specific questions about gastrointestinal distress (nausea, vomiting, diarrhea). If a medically substantial problem is reported, it should be reported to the Treating Physician immediately.

11.1.2 Signs

At screening, a physical exam of the head, eyes, ears, cardiovascular system, lungs, abdomen (liver/spleen), extremities, skin, lymphatic system, neuropsychiatric mental status and sensory/motor status, musculoskeletal system and general appearance will be performed. Height and weight will be recorded. Vital signs (blood pressure, heart rate, temperature) will be recorded. During treatment and follow up, a targeted physical exam will be performed if prompted by the subject or the subject's appearance. Vital signs will be recorded.

11.1.3 Laboratory Assessments

Venous blood will be collected during screening for measurement of hematology parameters to be reported [white blood cells (WBC), neutrophil count, hemoglobin, hematocrit, and platelet count] and chemistry parameters including glucose, sodium, potassium, creatinine, ALT, and bilirubin. These baseline values will be used to determine if the subject has a concomitant medical condition.

On nominal days 14 and 28, a blood sample will be collected for AST and creatinine only. On follow up visits at Month 3, Month 7, and Month 13, blood will again be collected for ALT and creatinine if on the previous sample the ALT value was above the upper limit of normal, or if the creatinine clearance was abnormal. Serum creatinine levels will be used to calculate creatinine clearance (CrCl) according to the Cockroft-Gault formula as follows:

Males	CrCl (mL/min) = [140 - age (years) x body weight (kg)] (72) x (serum creatinine [mg/dL])		
Females	$CrCl (mL/min) = 0.85 \times [140 - age (years) \times body weight (kg)]$		

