1 LIST OF ABBREVIATIONS AND DEFINITIONS

- AE adverse event
- ALT alanine transaminase
- BUN blood urea nitrogen
- CL cutaneous leishmaniasis
- CRF case report form
- CTC Common Terminology Criteria
- DCL diffuse cutaneous leishmaniasis
- DNA deoxyribonucleic acid
- ENT ear-nose-throat
- ECG electrocardiogram
- FDA food and drug administration
- IND investigational drug application
- IRB institutional review board
- mITT Modified Intention-to-treat
- ML mucosal leishmaniasis
- MSS mucosal severity score
- PCR polymerase chain reaction
- PE physical examination
- PI Principal Investigator
- SAE serious adverse event

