4.2.3 Warnings and Precautions

Impavido is contraindicated in pregnancy. Women of childbearing potential have to use effective contraception during and up to 3-6 months after treatment. Vomiting/diarrhea are very common/common side effects of therapy with Impavido and can compromise the efficacy of oral contraception. The subject must be informed by her physician of these symptoms and if necessary, suitable alternative methods of contraception must be used.

Subjects with ALT (liver function), serum creatinine, and blood urea nitrogen (BUN) (renal function) 1.25 times above the normal range were generally excluded from the clinical studies. Thus, data from subjects with abnormalities of liver and kidney function are not available.

Treatment with Impavido may lead to an increase in serum creatinine. Kidney function must be evaluated in biweekly intervals. In subjects with clinically significant abnormality in kidney function, monitoring should be continued until normalization.

Gastrointestinal symptoms such as nausea, vomiting, diarrhea, and a feeling of motion sickness are possible side effects of therapy with Impavido. The subjects must be instructed that in case of prolonged persistence of vomiting and diarrhea a sufficient fluid intake must be ensured, to avoid dehydration and consequently the risk of an impaired renal function.

Organ system	Very Common	Common	
	>10% of subjects	1-10% of pts	
Gastrointestinal	Nausea	Motion sickness	
	Vomiting Grade 1-2*	Diarrhea Grade 1*	
	ç	Headache	
Renal	Creatinine elevation		
	Grade 1*		

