9.3 Assessment During Miltefosine Treatment

9.3.1 Study Day 1

Study Day 1 visit is conducted on the first day of miltefosine therapy and includes:

- 1. Medical History record changes in medical history or medications since screening visit
- 2. Physical Examination form perform brief physical exam including vital signs
- 3. Pregnancy test form perform a pregnancy test in women of child bearing potential, unless the screening pregnancy test was performed within the previous 24 hours.
- 4. Complete the eligibility checklist to ascertain if the subject still meets all of the eligibility criteria, then the subject will receive the first dose of medicine.
- 5. Record any AEs

9.3.2 Study Days 7 and 14

Two visits are scheduled to occur between Study Day 2 through Study Day 27 and should preferably occur at the end of Study Week 1 and Study Week 2 with in a three-day window either side of Day 7 and Day 14. At these two visits the following assessments are performed:

- 1. Medical History The subject will return to clinic for evaluation; record any AEs
- 2. Treatment form complete log
- 3. If more medication than that which was dispensed on day 1 is needed, further medication will be dispensed on the nominal day 14 visit
- 4. Chemistry record values of ALT and creatinine in the serum (Day 14 visit only)
- 5. Record any AEs

9.3.3 Study Day 28

Study Day 28 visit is conducted the last day of miltefosine therapy and includes:

- 1. Medical History record changes in medical history or medications
- 2. Physical examination record vital signs
- 3. Interval History of leishmaniasis:
 - a. CL lesion reactions
 - b. ML evolution of symptoms
- 4. CL subjects: Re-examination of each CL lesion and re-recording the size of the lesion ulceration (length/width), other notable characteristics of the lesion

- 5. ML subjects: Re-examination of mucosal membranes
- 6. Pregnancy test in women of child-bearing potential
- 7. Chemistry record values of ALT and creatinine in the serum
- 8. Record any AEs

9.3.4 Study Week 6

Two weeks after the Study Day 28 visit record the following:

- 1. Medical History record changes in medical history or medications since 28-day visit
- 2. Physical examination perform brief physical exam if appropriate, and vital signs
- 3. Interval History of leishmaniasis since last visit to include:
 - a. ML re-examination of mucosal membranes. Evolution of symptoms

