 - b. CL subjects re-examination of each CL lesion and record the size of the lesion ulceration (length/width), other notable characteristics of the lesion
- 4. ALT and creatinine: Repeat if abnormal on last examination
- 5. Record any AEs

9.3.5 Study Month 3

Study Month 3 visit is conducted 2 months after the end of miltefosine therapy and includes:

- 1. Medical History record changes in medical history or medications since 6-week visit
- 2. Physical Examination perform brief physical exam if appropriate, and vital signs
- 3. Interval History of leishmaniasis since last visit to include:
 - a. ML re-examination of mucosal membranes. Evolution of symptoms.
 - b. CL subjects re-examination of each CL lesion and record the size of the lesion ulceration (length/width), other notable characteristics of the lesion
- 4. Pregnancy test in women of child bearing potential
- 5. ALT and creatinine: Repeat if abnormal on last examination
- 6. Record any AEs

9.3.6 Study Month 7

Study Month 7 visit is conducted 6 months after the end of miltefosine therapy. Final follow up visit for CL subjects and includes:

- 1. Medical History record changes in medical history or medications since 3-month visit
- 2. Physical Examination perform brief physical exam if appropriate, and vital signs
- 3. Interval History of leishmaniasis since last visit to include:
 - a. ML re-examination of mucosal membranes. Evolution of symptoms
 - b. CL subjects re-examination of each CL lesion and record the size of the lesion ulceration (length/width), other notable characteristics of the lesion
- 4. Pregnancy test in women of child bearing potential
- 5. ALT and creatinine: Repeat if abnormal on last examination
- 6. Record any AEs

9.3.7 Study Month 13

Study Month 13 visit is conducted 12 months after the end of miltefosine therapy. Final follow up visit for ML subjects and includes:

- 1. Medical History record changes in medical history or medications since 7-month visit
- 2. Physical Examination perform brief physical exam if appropriate, and vital signs

- 3. Interval History of leishmaniasis since last visit to include:
 - a. ML re-examination of mucosal membranes. Evolution of symptoms.
 - b. CL subjects re-examination of each CL lesion and record the size of the lesion ulceration (length/width), other notable characteristics of the lesion
- 4. ALT and creatinine: Repeat if abnormal on last examination
- 5. Record any AEs

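### Section 11.1.3 names AST where ALT is meant, prints a creatinine clearance that is always negative and omits the Week 6 recheck; 9.3.2 and 11.1.4 leave out on-treatment pregnancy tests that the schedule marks

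*Combined protocol and SAP*

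**What the plan says.** **On-treatment chemistry.** Section 11.1.3 reads "On nominal days 14 and 28, a blood sample will be collected for AST and creatinine only". For the same visits, footnote f of the Time and Event Schedule (Sections 2 and 9) specifies ALT and creatinine. Section 9.3.2 has "Chemistry record values of ALT and creatinine in the serum (Day 14 visit only", and 9.3.3 repeats ALT and creatinine for Day 28.

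**Creatinine clearance.** Section 11.1.3 says clearance is computed by Cockcroft-Gault and prints the numerator, for males and females alike, as one bracket containing "140 - age (years) x body weight (kg". Besides an ALT above the normal limit, the trigger for repeat sampling is "or if the creatinine clearance was abnormal".

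**Repeat visits.** Section 11.1.3: "On follow up visits at Month 3, Month 7, and Month 13, blood will again be collected for ALT and creatinine". Week 6 is not listed. The schedule marks Week 6 chemistry under footnote g, and 9.3.4 has "ALT and creatinine: Repeat if abnormal on last examination".

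**Pregnancy tests.** Both copies of the schedule mark tests at screening, Days 1, 7, 14 and 28, and Months 3 and 7. Section 9.3.1 includes Day 1 (waived if the screening test was within 24 hours) and 9.3.3 includes Day 28. The five-item list for Days 7 and 14 in 9.3.2 has no pregnancy test. Section 11.1.4 names screening, end of treatment and follow-up.

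**The concern.** Each Treating Physician carries out the protocol for his or her own subject, and no clause says whether the schedule or the text prevails where they differ. A site that follows 11.1.3 literally would draw the wrong enzyme. It would then have no on-treatment ALT for the change-from-baseline summaries in 12.8, and no baseline AST to compare with, because the screening panel contains ALT and not AST. Its computed clearance could not serve the repeat trigger that depends on it.

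Read alone, 11.1.3 also delays the first recheck of an abnormal Day 28 result. Section 4.2.3 asks that after a clinically significant kidney abnormality "monitoring should be continued until normalization". Creatinine rises are expected: Table 2 reports them in 29 of 89 miltefosine recipients (33%) against 4 of 44 on placebo (9%).

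The pregnancy tests matter for a different reason. The drug is contraindicated in pregnancy (4.2.3), and 8.6 makes a positive test during active treatment a ground for withdrawal. A test first repeated on Day 28, the last treatment day, comes too late to prevent exposure.

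**Working it through.** **1. Which enzyme.** Setting the places side by side:

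| Place | Enzyme |
|---|---|
| Screening panel (9.2, 11.1.3) | ALT |
| Schedule footnote f, Days 14 and 28 | ALT |
| 9.3.2 (Day 14), 9.3.3 (Day 28) | ALT |
| 11.1.3, Days 14 and 28 | AST |
| 11.1.3, repeat trigger | ALT |
| 11.3, grading table | ALT |

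The abbreviation list has "ALT alanine transaminase" and no entry for AST. AST appears elsewhere only in 4.2.6, describing who was excluded from earlier studies. The sentence in 11.1.3 restricts the sample to AST and creatinine, so a Day 28 sample drawn to that instruction holds no ALT value for the repeat rule in the next sentence to act on.

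**2. Clearance.** Inputs: age at least 18 and weight at least 30 kg (7.1.2), with denominator 72 × serum creatinine. Creatinine values of 1.0 and 2.0 mg/dL are illustrative; the sign does not depend on them.

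- As printed: CrCl = [140 − age × weight] / (72 × creatinine), × 0.85 for females.
- Corrected: CrCl = (140 − age) × weight / (72 × creatinine), × 0.85 for females.

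The printed bracket falls as age or weight rises, so its maximum over eligible subjects is 140 − 18 × 30 = −400. At age 18 it is non-negative only at or below 140/18 = 7.8 kg; at 30 kg, only at or below 140/30 = 4.7 years. Both lie outside eligibility.

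| Subject | Creatinine (mg/dL) | As printed (mL/min) | Corrected (mL/min) |
|---|---|---|---|
| Male, 18 y, 30 kg | 1.0 | −400/72 = −5.6 | 122 × 30/72 = 50.8 |
| Female, 18 y, 30 kg | 1.0 | 0.85 × (−400)/72 = −4.7 | 0.85 × 3660/72 = 43.2 |
| Male, 40 y, 70 kg | 1.0 | (140 − 2800)/72 = −36.9 | 100 × 70/72 = 97.2 |
| Male, 40 y, 70 kg | 2.0 | −2660/144 = −18.5 | 7000/144 = 48.6 |

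The last two rows show that the printed value rises when creatinine doubles, the opposite of what a clearance should do.

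**3. First recheck of an abnormal Day 28 value.** Under 9.3.4 it is at Week 6, 2 weeks after therapy. Under 11.1.3 alone it is at Month 3, 2 months (about 8 weeks) after therapy, which is about 6 weeks later.

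**4. Longest gap between scheduled on-treatment pregnancy tests.**

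- Schedule: 28 − 14 = 14 days nominal; 28 − 11 = 17 days if the Day 14 visit uses the full 3-day window early.
- 9.3.1 to 9.3.3 as listed: 28 − 1 = 27 days; up to about 28 since the last test if Day 1 is waived for a screening test up to 24 hours before.

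**The case against.** The best reply is that these are typographical slips, already correct elsewhere. ALT at Days 14 and 28 is stated in footnote f and twice in 9.3. The Week 6 repeat is in footnote g and 9.3.4, and 11.1.3 does not say its list of visits is exhaustive. The schedule sits within Section 9, so Section 9 read as a whole does require the Day 7 and Day 14 pregnancy tests. Cockcroft-Gault is named, and a negative clearance is obviously impossible. Clearance feeds only the repeat trigger; eligibility and adverse-event grading use serum creatinine. If abnormal means too low, a negative value would lead to more retesting, not less.

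Most of this stands and limits the severity. The recheck delay and the 27-day gap arise only if the text is read without the schedule, and the window in 9.3.2 behind the 17-day figure is worded there as a preference. Pregnancy risk is also reduced by required contraception and by advice to seek testing on suspicion. But none of this makes the printed analyte or formula right. A trigger that flags everyone, or that each site repairs for itself, does not do what 11.1.3 intends.

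Two further objections have some force. The schedule marks, not the text, could be the error for pregnancy tests. That is unlikely: both copies of the schedule agree, and 11.1.4 also omits the Day 1 test that 9.3.1 requires, so 11.1.4 is incomplete in any case. Second, the plan never defines abnormal clearance, and 9.3.4 to 9.3.7 refer to abnormal creatinine instead. That question stays open after the correction proposed here.

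**Conclusion.** The concern holds in all four parts. The AST instruction conflicts with every other statement of the test. The clearance formula gives a negative result for every eligible subject, an exact consequence of the bracket as printed and the age and weight minima. The Week 6 recheck is missing from 11.1.3, a delay of about 6 weeks if that section is used alone. The Day 7 and Day 14 pregnancy tests are missing from 9.3.2, and those plus Day 1 from 11.1.4. The longest on-treatment gap is then 27 days instead of a nominal 14 if 9.3.1 to 9.3.3 are followed without the schedule.

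The cure endpoints are untouched and the schedule already carries the right tests, so this should be corrected but does not threaten the study's conclusions. The pregnancy-test omission is the part with the most direct bearing on subjects' safety.

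**What to change.** In 11.1.3:

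- Replace AST with ALT for Days 14 and 28.
- Write CrCl = (140 − age) × weight / (72 × serum creatinine), multiplied by 0.85 for females.
- Add Week 6 to the repeat visits.
- Leave the clearance trigger as it is.

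In 9.3.2, add the Day 7 and Day 14 pregnancy tests. In 11.1.4, add Days 1, 7 and 14.

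The cost is a text correction in three sections. Every test and visit named is already in the schedule, so no procedure is added beyond it.

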11.1.4 Pregnancy Test

For females of child-bearing potential, an FDA-cleared serum or urine pregnancy test that measures human β -chorionic gonadotropin will be used during screening, at the end of treatment, and during follow up.

(72) x (serum creatinine [mg/dL])

11.1.5 Electrocardiogram (ECG)

An ECG will be taken during screening to evaluate if the subject has a baseline medical condition.

11.2 AE Definition

An AE is defined as any reaction, side effect, or untoward event that occurs during the course of the clinical trial, whether or not the event is considered investigational product-related or clinically significant. For this study, AEs will include events reported by the subject, as well as clinically significant abnormal findings on physical examination or laboratory evaluation.

A new illness, symptom, sign, or clinically significant clinical laboratory abnormality is considered an AE. A worsening of a pre-existing condition or abnormality is also considered an AE. The appearance of scars at healed lesion sites will not be reported as an AE. Stable chronic conditions which are present prior to clinical trial entry and do not worsen are not considered AEs.

11.4 Assessment of Causality

The relatedness of an AE to the investigational product is the best estimate of the causal relationship between the investigational product and an AE at the time of reporting. Causality will be assessed by the Treating Physician and subsequently by the PI.

Definitions are:

Unrelated:	There is no temporal relationship between the event and the administration of the investigational product or the event is clearly due to the subject's medical condition, other therapies, or accident.	
Unlikely:	There is evidence of exposure to the investigational product but there is another more likely cause of the event.	
Possibly Related:	There is some temporal relationship between the event and the administration of the investigational product and the event is unlikely to be explained by the subject's medical condition or other therapies.	
Probably Related:	The temporal relationship between the event and the administration of the investigational product is compelling, and the subject's medical condition and other therapies cannot explain the event.	
Definitely Related:	The event follows a reasonable temporal sequence from administration of the medication or follows a known or suspected response pattern to the medication.	

The categories of Definitely Related, Probably Related, and Possibly Related will be considered investigational product related with regards to summary statistics.

11.5 AE Actions and Outcomes

For each AE that is reported, the actions taken with respect to investigational product can be:

- 1. none
- 2. permanently discontinued

Also, outcomes will be recorded as:

- 1. resolved
- 2. resolved with sequelae
- 3. ongoing
- 4. required treatment
- 5. unknown

11.6 Monitoring and Reporting of Adverse Events

The Treating Physician will monitor subjects for the occurrence of AEs from time the first investigational product is taken on Day 1 through the end of follow up at Month 7 for CL or Month 13 for ML. For the period between Study Day 1 and Study Week 6 (2 weeks after the end of therapy), all AEs regardless of seriousness or relationship to the investigational product are to

be recorded on the CRF. For the period Week 6 to Month 7 for CL, or Month 13 for ML, only AEs requiring medical attention are to be recorded on the CRF.

Whenever possible, symptoms should be grouped as a single syndrome or diagnosis. The Treating Physician should specify the date of onset, maximum severity grade, his/her opinion as to association between the AE and the administration of the investigational product (causality), outcomes including corrective therapy given (if applicable). Clinically significant AEs ongoing at the last follow up visit will be followed to resolution or stabilized including the administration of any concomitant medications.

11.7 Serious Adverse Event (SAE)

Each AE or reaction will be classified by the Treating Physician as serious or non-serious. Based on the seriousness of the AE or reaction appropriate reporting procedures will be followed. An SAE is defined as:

- results in death;
- is life-threatening; (NOTE: The term "life-threatening" in the definition of "serious" refers to an event in which the subject was at risk of death at the time of the event; it does not refer to an event which hypothetically might have caused death if it were more severe.)
- requires inpatient hospitalization or prolongation of existing hospitalization;
- results in persistent or significant disability/incapacity; or
- is a congenital anomaly/birth defect.

In addition, important medical events that may not result in death, be life-threatening, or require hospitalization may be considered a serious adverse drug reaction, when based on appropriate medical judgment that may jeopardize the subject and may require medical or surgical intervention to prevent one of the outcomes listed in the above definition. For this protocol, becoming pregnant between Study Day 1 and Month 7 is considered to be an SAE.

11.8 SAE Reporting Requirements

The Treating Physician must report all SAEs to the PI that are possibly, probably, or definitely related to study medication within 24-hours of learning of the SAE by email, telephone, or fax.

Within a further 3 working days, the SAE CRF, along with any other appropriate supporting documentation, must be submitted by the Treating Physician to the PI.

The Data Management Center will prepare a narrative or a MedWatch (FDA Form 3500A) if the SAE meets the criteria for expedited reporting for an SAE.

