14.2 Data Collection and Monitoring

Data will be collected at the study site in the subject's medical records, which will be transcribed at the site on to the study CRFs provided by the data management center. CRFs are to be completed on an ongoing basis according to the instructions in the Study Procedures Manual.

The Treating Physician will be responsible for completing the CRFs, verifying the accuracy of the CRF data versus the source documentation, and sending the completed CRFs to the data management center.

The Treating Physician will correspond with the PI at the following time points:

- prior to obtaining informed consent to verify subject eligibility,
- Study Day 28 or Week 6 follow-up visit,
- Month 7 follow up for CL subjects, or Month 7 and 13 for ML subjects.

Completed CRFs should be submitted to the data management center prior to the Treating Physician contacting the PI by telephone. The purpose of these communications between Treating Physician and PI is to assure optimum subject care and conveyance of study data.

The Treating Physician and PI can also correspond with each other at any other time of their choosing.

In spite of these interactions and advice that may be offered by the PI, clinical responsibility for subject care rests with the Treating Physician.

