15 ROLES AND RESPONSIBILITIES OF STUDY PERSONNEL

15.1 Principal Investigator

Signs the protocol agreement, below, and the Form FDA 1572. The PI is responsible for passage of the protocol and any amendments through a "central" IRB before starting the study. The PI is responsible for interaction with Treatment Physicians to ensure protocol adherence and data integrity, and overall coordination of the study.

The PI is also responsible for participating in safety evaluations of subjects during the conduct of the study. The PI will review all unanticipated problems involving risk to subjects or to others, SAEs, and all subjects' deaths associated with the protocol, and provide an unbiased written report of the event. At a minimum, the PI should comment on the outcomes of the event or problem and, in the case of a SAE or death, comment on the relationship to participation in the study. The PI should also indicate whether he/she concurs with the details of the report provided by the Treating Physician. Reports for SAEs determined by either the Treating Physician or PI to be possibly, probably, or definitely related to participation and reports of events resulting in death should be promptly forwarded to the Sponsor and the "central" IRB.

The PI is responsible for filing a final clinical study report with the Sponsor.

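### Section 11.8 limits the 24-hour SAE report to events judged drug-related, so SAEs judged unrelated or unlikely, including deaths and pregnancies, have no stated deadline for reaching the PI

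*Combined protocol and SAP*

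**What the plan says.** Section 11.7 has the Treating Physician classify each event as serious or not, and links reporting to that classification: "Based on the seriousness of the AE or reaction appropriate reporting procedures will be followed". Death is on its list of SAE criteria. It then adds: "For this protocol, becoming pregnant between Study Day 1 and Month 7 is considered to be an SAE". Neither carries a causality condition.

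Section 11.8 sets the only timed route from the physician to the PI: "The Treating Physician must report all SAEs to the PI that are possibly, probably, or definitely related to study medication within 24-hours". The clock starts when the physician learns of the event. The SAE CRF and supporting papers follow within three more working days, a clock that runs on from the first report.

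Section 11.4 defines five causality categories, from unrelated to definitely related, and names two assessors in sequence: "Causality will be assessed by the Treating Physician and subsequently by the PI".

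Section 15.1 gives the PI duties that are wider than the 11.8 trigger. On review: "The PI will review all unanticipated problems involving risk to subjects or to others, SAEs" and deaths associated with the protocol. On forwarding to the Sponsor and the central IRB, it covers "Reports for SAEs determined by either the Treating Physician or PI to be possibly, probably, or definitely related to participation", and separately "reports of events resulting in death should be promptly forwarded to the Sponsor", whatever their cause.

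On routine data flow, Section 14.2 says: "CRFs are to be completed on an ongoing basis according to the instructions in the Study Procedures Manual". It requires physician-PI contact after dosing starts at Day 28 or Week 6, at Month 7, and at Month 13 for ML subjects. Contact at other times is optional.

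**The concern.** The 24-hour duty depends on a causality judgement that, before any report is made, only the Treating Physician is in a position to make. If that physician decides an SAE is unrelated or unlikely to be related, 11.8 imposes no prompt duty to tell the PI. The PI's later assessment exists partly to catch a mistaken first judgement, and it cannot do so until the PI knows of the event. Likewise, the PI cannot promptly forward a death that has not been reported.

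Pregnancy shows the difficulty most clearly. Section 4.2.7.1 reports embryotoxic, fetotoxic and teratogenic risk in rats, so the concern is fetal exposure. The 11.8 trigger asks a different question: whether the drug caused the event. One physician could reasonably say it did not. Another could say it did, because Section 4.2.6 notes that vomiting and diarrhea can undermine oral contraception. Whether the PI hears within 24 hours then rests on one person's opinion.

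What is at stake is the timeliness of central safety oversight. Efficacy endpoints are untouched, SAEs judged related are already covered at 24 hours, and Section 12.8 lists and narrates SAEs whatever their causality.

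**Working it through.** The protocol gives no figure to reproduce here. The check has two parts: a search for any other timed route to the PI, and the waits implied by the required contacts.

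**1. Routes to the PI for an SAE judged unrelated or unlikely**

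| Section | What it provides | Deadline to the PI? |
|---|---|---|
| 11.8, initial report | Only SAEs judged possibly, probably or definitely related | Not for these SAEs |
| 11.8, SAE CRF | Three further working days after the initial report | No, the clock has no start |
| 11.6 | All AEs recorded on the CRF to Week 6; after that, only those needing medical attention | No |
| 14.2 | Ongoing CRF completion; CRFs sent to the data management center before the PI contacts; optional extra contact | No, apart from the scheduled contacts |
| 14.3 | Data reviewed on receipt, with no stated duty to alert the PI | No |
| 15.1 | PI review and onward forwarding | No, it governs the step from PI to Sponsor and IRB |
| 15.3 | Physician reports AEs; no recipient or time given | No |
| 8.6 | Pregnancy followed to its end if possible | No |

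The scheduled contacts in 14.2 are the only dated points at which the PI must hear from the physician.

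**2. Wait until the next required contact**

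Assumptions: visits fall on nominal days; one month = 365.25/12 = 30.44 days; Day 28 is the end of therapy; the wait starts when the physician learns of the event, as in 11.8; there is no voluntary contact.

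- Week 6 = 28 + 14 = Day 42
- Month 3 = 28 + 2 × 30.44 = Day 88.9
- Month 7 = 28 + 6 × 30.44 = Day 210.6
- Month 13 = 28 + 12 × 30.44 = Day 393.3

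Wait = day of next required contact − day learned:

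| Learned at | Wait in days |
|---|---|
| Day 7 | 28 − 7 = 21, or 42 − 7 = 35 if the contact is at Week 6 |
| Day 14 | 28 − 14 = 14, or 42 − 14 = 28 |
| Day 28 | 0, or 42 − 28 = 14 |
| Week 6 | 0, or 210.6 − 42 = 168.6 if the early contact was already made at Day 28 |
| Month 3 | 210.6 − 88.9 = about 122 |
| Month 7, or Month 13 for ML | 0 |

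The outer bounds apply if the physician learns of the event just after a contact:

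- Week 6 to Month 7: 210.6 − 42 = 168.6 days
- Day 28 to Month 7: 210.6 − 28 = 182.6 days
- Month 7 to Month 13 (ML): 393.3 − 210.6 = about 183 days

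The Month 3 row matters in practice because Section 9.3.5 schedules a pregnancy test at that visit and 14.2 requires no PI contact there.

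**The case against.** The best defence is that 11.7 and 11.8 can coexist. Section 11.7 promises only suitable procedures based on seriousness and names no deadline, so 11.8 can be read as a fast track for the related subset. Section 15.1 uses the same relatedness threshold for forwarding, which suggests the filter was deliberate. This part stands: there is no literal contradiction between 11.7 and 11.8, nor with 11.4 or 15.1. The gap is functional. Section 15.1 lets either assessor call an event related and treats deaths separately, and 11.8 does not give the PI timely notice of either.

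Second, the Study Procedures Manual may set an SAE deadline. That is possible and cannot be checked, because the Manual is not among the documents. It would not remove the restriction written into 11.8.

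Third, the day counts are worst cases. They need a judgement of unrelated or unlikely, no voluntary contact, and no alert from CRF review, and the documents give no likelihood for any of these. They also assume the subject stays on the visit schedule, so they do not measure the delay after a death and are uncertain for a pregnancy that leads to withdrawal during treatment. All of this is accepted, and the figures should be read as illustrative bounds.

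Fourth, the subject's own care does not wait for the PI, since Sections 13.3 and 14.2 place clinical responsibility with the Treating Physician. That is correct. It limits the possible harm to delayed oversight.

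Finally, 11.8 does not say whose causality judgement applies. That it is the Treating Physician's is an inference, but a firm one: the physician is the reporter, and 11.4 places the PI's assessment second.

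**Conclusion.** The concern holds as a weakness in a stated rule. In the documents available, SAEs judged unrelated or unlikely have no deadline for reaching the PI, and this includes deaths and the pregnancies that 11.7 makes SAEs. Following 11.8 as written lets the first assessor's opinion delay both the PI's second assessment and the prompt forwarding of deaths.

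If only the required contacts are used, the wait is about 122 days for a pregnancy found at Month 3, with outer bounds of about 169 to 183 days, compared with 24 hours for SAEs judged related. These figures rest on nominal visit days, a 30.44-day month and no voluntary contact. Actual delays may be much shorter. The harm is possible delay only, and the point is a cheap improvement to safety oversight.

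**What to change.** Reword Section 11.8 so that the physician's 24-hour report to the PI covers every SAE as defined in 11.7, naming deaths and pregnancies, whatever the causality judgement. State that the SAE CRF is due within three further working days for the same events. Both existing intervals and the reporting channels stay as they are. Section 15.1 needs no change, because its review and forwarding rules already cover these events once the PI has the report.

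The cost is one reworded paragraph plus some extra reports for SAEs judged unrelated or unlikely. The documents give no SAE rate. Assuming that 1% to 10% of subjects have such an event, and using the planned 10 to 20 subjects a year, the extra load runs from 10 × 0.01 = 0.1 to 20 × 0.10 = 2 reports a year.
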